**PROTOCOL SYNOPSIS:**

Study Title	A Single-Center, Open-Label Study to Evaluate Tralokinumab in Atopic Dermatitis Subjects Who Experienced Inadequate Response on Dupilumab
Sponsors	[name]
Study Objectives	
Primary Objective: To assess efficacy of tralokinumab in subjects who had an inadequate response to dupilumab
 
Secondary Objective: To assess safety and patient satisfaction of tralokinumab in subjects who had an inadequate response to dupilumab

Study Design	
24-week study of 20 atopic dermatitis patients who have been treated with dupilumab will receive Tralokinumab 600mg at week 0 followed by 300mg Q2W for 24 weeks.
 
Baseline characteristics for Dupilumab treatment will be captured including IGA, BSA, prior and concomitant therapy as well as Baseline characteristics at tralokinumab initiation.
 
Atopic Dermatitis will be confirmed at screening using the Hanifin and Rajka (1980) diagnostic criteria for AD.
 
A target lesion representative of subject's disease will be selected by the investigator at baseline and photographed throughout the study.

Study Centers	
Eczema Treatment Center of New Jersey
 
[name]

Study Population	Adult male and female subjects with moderate-to-severe atopic dermatitis
Main Inclusion Criteria	
Subjects must meet the following criteria to be enrolled in this study:
 
 
1. Male or female adult <math>\geq</math> 18 years of age;
 
2. All participants must have prior treatment with dupilumab for atopic dermatitis meeting one of the following conditions: 
 
• Participants who stopped dupilumab treatment due to non-response, partial response, loss of efficacy must have been previously treated with dupilumab for at least 12 weeks.
 
• Participants who stopped dupilumab treatment due to intolerance or AEs to the drug may enter the study with no required prior length of dupilumab treatment. AE's must be resolved prior to 1st tralokinumab dose.
 
 
 
3. Females of childbearing potential (FCBP) must have a negative urine pregnancy test at Baseline. FCBP who engage in activity in which conception is possible must use one of the approved contraceptive options: hormonal contraception; intrauterine device (IUD); tubal ligation; or partner's vasectomy; Male or female condom diaphragm with spermicide, cervical cap with spermicide, or contraceptive sponge with spermicide.
 

	
4. Subject is a candidate for systemic therapy.
 
5. Subject must be in general good health as judged by the Investigator, based on medical history, physical examination.
 
6. Able and willing to give written informed consent prior to performance of any study-related procedures.

Main Exclusion Criteria	
Subjects who meet any of the following criteria will be excluded from participation in this study:
 
 
1. Subjects with previous exposure to tralokinumab.
 
2. Known or suspected hypersensitivity to tralokinumab or any of its excipients.
 
3. Women of childbearing potential who are pregnant, intend to become pregnant, or are lactating.
 
4. Use of tanning beds or phototherapy within 4 weeks of baseline
 
5. Use of systemic therapies (systemic steroids, cyclosporine, oral JAK inhibitors etc.) for atopic dermatitis within 4 weeks
 
6. Patient non-compliant with Dupixent dosing based on investigator discretion.
 
7. Any clinically significant (as determined by the investigator) cardiac, endocrinologic, pulmonary, neurologic, psychiatric, hepatic, renal, hematologic, immunologic disease, or other major disease that is uncontrolled.
 

Study Visits	
Screening
 
Week 0
 
Week 4
 
Week 8
 
Week 12
 
Week 16
 
Week 20
 
Week 24

Study Endpoints	
Primary Endpoints:
 
Proportion of subjects achieving IGA 0 or 1 at week 16
 
Secondary Endpoints:
 
Proportion of subjects achieving IGA 0 or 1 at weeks 20, 24
 
Proportion of patients achieving 50% reduction in BSA at weeks 12, 16, 20 and 24
 
IGA, BSA, Pruritis NRS and DLQI improvement at weeks 0, 4, 8, 12, 16, 20 and 24
 
Adverse Events/Serious Adverse Events (SAE's)

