### **3.2 Rationale for Treating Atopic Dermatitis with Tralokinumab**

Tralokinumab, a fully human monoclonal antibody, specifically neutralizes interleukin-13, a key cytokine driving peripheral inflammation in atopic dermatitis (AD). In phase II studies, tralokinumab combined with topical corticosteroids provided early and sustained improvements in AD signs and symptoms. In two 52-week, randomized, double-blind, placebo-controlled, phase III trials, ECZTRA 1 and ECZTRA 2, adults with moderate-to-severe AD were randomized (3 : 1) to subcutaneous tralokinumab 300 mg every 2 weeks (Q2W) or placebo. Tralokinumab monotherapy was superior to placebo at 16 weeks of treatment and was well tolerated up to 52 weeks of treatment. Dupilumab, a parenterally administered inhibitor of IL-4 and IL-13, is the first biologic drug approved for use in adults with moderate-to-severe atopic dermatitis. While Phase III trials showed improvement in AD symptoms and itch for patients with atopic dermatitis, many patients fail to achieve and/or maintain satisfactory efficacy, have an intolerance to dupilumab treatment or are unable to continue treatment related to insurance coverage. This study aims to explore the effectiveness and safety of tralokinumab (ADBRY) in patients previously exposed to dupilumab for atopic dermatitis.

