## **4. STUDY OBJECTIVE**

To explore the effectiveness and safety of tralokinumab in subjects who have previously used dupilumab for the treatment of moderate-to-severe atopic dermatitis

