## **5. INVESTIGATIONAL PLAN**

### **5.1 Overall Study Design and Plan**

20 adult subjects with moderate-to-severe atopic with previous exposure to dupilumab will receive tralokinumab loading dose of 600mg (4 150mg syringes) at week 0 followed by tralokinumab 300mg (2 150mg syringes) Q2W for 24 weeks.

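### The objective names inadequate responders to dupilumab, but criterion 2 also admits intolerance/AE stoppers, and the primary week-16 proportion pools the two groups

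*Combined protocol and SAP*

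**What the plan says.** - **Title and objectives (Protocol Synopsis).** The title refers to "Subjects Who Experienced Inadequate Response on Dupilumab". The primary objective is "To assess efficacy of tralokinumab in subjects who had an inadequate response to dupilumab" and the secondary objective is "To assess safety and patient satisfaction of tralokinumab in subjects who had an inadequate response to dupilumab".
- **Eligibility (Synopsis and Section 5.2.1, criterion 2).** There are two ways in. The first is for those who "stopped dupilumab treatment due to non-response, partial response, loss of efficacy must have been previously treated with dupilumab for at least 12 weeks". The second is for those who came off dupilumab because of intolerance or adverse events. It sets no minimum exposure and does not mention response.
- **Looser wording elsewhere.** Section 4 speaks of effectiveness and safety "in subjects who have previously used dupilumab for the treatment of moderate-to-severe atopic dermatitis". The aim that closes Section 3.2 is worded "in patients previously exposed to dupilumab for atopic dermatitis", and Section 5.1 says that subjects "with previous exposure to dupilumab will receive tralokinumab".
- **Background (Section 3.2).** Many patients on dupilumab are said to "fail to achieve and/or maintain satisfactory efficacy, have an intolerance to dupilumab treatment or are unable to continue treatment related to insurance coverage". Intolerance stands here as an item separate from failure of efficacy.
- **Analysis (Synopsis endpoints and Section 8.2).** The primary endpoint is a single proportion with IGA 0 or 1 at week 16. No subgroup or split by reason for stopping is planned. Section 8.2.1 leaves anything further to an optional separate plan.

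**The concern.** The objective and the enrolled population do not match. Someone who stopped dupilumab early for an adverse event may have been responding well, or may have stopped before response could be judged. That person is eligible and counts in the primary proportion, but need not belong to the population named in the objective. Nothing fixes or caps the share of such subjects, so enrolment decides the mix that the headline figure describes.

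The study is single-arm and open-label, with about 20 subjects and no comparator, test or threshold. No decision rule can be invalidated. What is at stake is the statement the study exists to make: a response rate, and for whom it holds.

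**Working it through.** **Figure to reproduce.** There is none. The plan gives no response rate, expected mix, precision target or basis for the sample size of 20. The check is a comparison of texts, followed by algebra and illustrations on assumed numbers.

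**Step 1: texts side by side.**

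| Place | Population |
|---|---|
| Title; synopsis primary and secondary objectives | Inadequate response to dupilumab |
| Criterion 2, first branch | Stopped for lack of efficacy, at least 12 weeks of dupilumab |
| Criterion 2, second branch | Stopped for intolerance/AEs, any exposure, no response condition |
| Section 3.2 aim; Sections 4 and 5.1 | Previous use or exposure |

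Rows one and three conflict unless the term is meant to include intolerance, and no section says that it does. Row four is true of everyone admitted under rows two and three. It is looser wording, not a second conflict.

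**Step 2: what the pooled rate measures.** Let s be the intolerance/AE share, and p_EFF and p_INT the week-16 rates in the two groups.

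Pooled = (1 − s) × p_EFF + s × p_INT

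Pooled − p_EFF = s × (p_INT − p_EFF)

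Assumed rates, for illustration only:
- p_EFF 20%, p_INT 50%, s = 0.25: 0.25 × 30 = 7.5 points, pooled 27.5%.
- The same rates, s = 0.5: 0.5 × 30 = 15 points, pooled 35%.
- Both rates 30%: difference 0 at any s.

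**Step 3: what a pooled result alone leaves open.** Suppose 5/20 (25%) is observed with m intolerance/AE stoppers. Responders among the 20 − m efficacy stoppers lie between max(0, 5 − m) and min(5, 20 − m).

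| m | Compatible efficacy-stopper result |
|---|---|
| 1 | 4/19 (21.1%) to 5/19 (26.3%) |
| 4 | 1/16 (6.3%) to 5/16 (31.3%) |
| 8 | 0/12 (0%) to 5/12 (41.7%) |

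**Step 4: reason for stopping is not response status.** Take 3/16 efficacy stoppers (18.8%) and 2/4 intolerance/AE stoppers (50%) responding, so 5/20 (25%) pooled. If all four intolerance/AE stoppers had also responded inadequately to dupilumab, the inadequate-responder rate would be the pooled 25%, not 18.8%. If none had, it would be 18.8%. The efficacy-stopper row is therefore the closest available figure under a narrow reading, but it is not the inadequate-responder rate by definition.

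**Step 5: precision of a split.** Exact (Clopper-Pearson) 95% limits for x/n are the 0.025 quantile of Beta(x, n − x + 1) and the 0.975 quantile of Beta(x + 1, n − x).

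| Result | 95% CI |
|---|---|
| 5/20 (all) | 8.7% to 49.1% |
| 4/16 and 1/4 | 7.3% to 52.4%; 0.6% to 80.6% |
| 3/12 and 2/8 | 5.5% to 57.2%; 3.2% to 65.1% |

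Each pair adds up to 5/20. Power to separate an assumed 20% from 50% is about 28% with 10 against 10 (normal approximation), so a between-group test would have little value.

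**The case against.** **Criterion 2 may be the working definition.** On that reading everyone enrolled is an inadequate responder and the pooled rate answers the objective. The reading is possible, but no section states it. Section 3.2 lists intolerance apart from failure of efficacy, and criterion 2 gives the two groups different exposure rules. One sentence from the sponsor would settle it.

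**Wording alone would cure the conflict, and 20 subjects are too few to split.** The first half stands: if the objective is reworded to the enrolled population, the pooled rate answers it and the rows only support it. The second half is a reason not to test between groups. It is not a reason to leave undescribed who was studied and how each group did.

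**The reason for stopping is not listed as collected data.** This stands. The synopsis lists IGA, BSA and prior and concomitant therapy for the dupilumab period, and Section 5.6.3 covers other previous treatments within the last 6 months. Neither names the reason for stopping. It must be known to apply criterion 2, but a field has to be added for it.

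**Stronger readings that the documents do not support.** A reader might infer three conflicting populations, but previous use or exposure is true of every eligible subject. A reader might treat the insurance remark in Section 3.2 as a further eligible group, but it is background on why patients leave dupilumab and does not say who enrols. A reader might also infer that, if intolerance is excluded, the pooled rate equals the inadequate-responder rate only when no intolerance/AE stoppers enrol or both groups respond alike. Step 4 of the working shows that this is wrong.

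**Conclusion.** The concern holds as a mismatch between the stated objective and the population that is enrolled and analysed. Followed as written, the plan would present a mixed-population rate as an answer about inadequate responders, unless the term is defined to include intolerance.

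The effect on the result cannot be sized. It depends on the intolerance/AE share, on the two group rates, and on how many intolerance/AE stoppers had also responded inadequately. The documents give none of these. The difference could go either way or be zero, so a claim that the pooled rate is biased in a particular direction would go beyond the text. The 5/20 result, the group sizes and the response rates used above are assumptions.

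This is a cheap improvement to what the study can say and about whom. It does not invalidate the design.

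**What to change.** 1. **Wording.** Reconcile the title, both synopsis objectives, Section 4 and criterion 2 to one stated target population, and align the looser phrasing in Sections 3.2 and 5.1. State whether inadequate response includes stopping for intolerance or AEs. Eligibility need not change.
2. **Section 8.2.** Keep the all-enrolled week-16 IGA 0/1 proportion as primary. Add two descriptive rows, each n/N with an exact 95% CI: efficacy stoppers (non-response, partial response or loss of efficacy) and intolerance/AE stoppers. The rows should add up to the all-enrolled row. Make no between-group test. Label the rows by reason for stopping, not as responders and non-responders.
3. **Data.** Record the reason or reasons for stopping dupilumab before the first tralokinumab dose, with a preset rule for subjects who have both.
4. **Reporting.** If the objective keeps its wording without including intolerance, do not present the pooled rate alone as the inadequate-responder rate. Cite the efficacy-stopper row and state its limit: some intolerance/AE stoppers may also have responded inadequately, or stopped too early to be assessed. If the term is defined to include intolerance, or the objective is reworded to the enrolled population, the pooled rate answers it and the rows are supporting description.

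**Cost.** A wording amendment through the IRB, one data field and one table, with no extra subjects or visits. The intervals will be wide, and the rows cannot show whether the groups differ.

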## 2 ETHICS AND REGULATORY OBLIGATIONS

## **2.1 Institutional Review Board (IRB)**

Written IRB approval of this protocol must be obtained before the study is initiated. Compliance with Title 21 of the US Code of Federal Regulations (CFR), Part 56, is required in order to protect the rights and welfare of human subjects involved in this study.

## **2.2 Ethical Conduct of the Study**

The study will be conducted in accordance with the ethical principles that have their origins in the Declaration of Helsinki and its amendments. In addition, the study will be performed in compliance with Good Clinical Practices (GCP), including the archiving of essential documents.

## **2.3 Subject Information and Consent**

The Informed Consent Form will be reviewed and approved by the IRB. The purpose, duration and possible risks and benefits will be explained to each potential subject. Consent in writing must be obtained from the subject before enrollment into the study. Consents will be signed and dated as required by Title 21 of CFR, Part 50. The consent will also comply with the requirements of the Health Insurance Portability and Accountability Act (HIPAA). The original, signed Informed Consent Form will be retained by the Investigator. A signed copy of the Informed Consent Form will be given to the subject. Each subject will be assigned a subject number that will be used in lieu of the subject's name on further research documentation.

# **3 INTRODUCTION**

## **3.1 Overview of Atopic Dermatitis**

Atopic Dermatitis (AD) or eczema is a common chronic inflammatory skin disease with a prevalence of 2-10% in adults. AD is often associated with other atopic disorders, such as rhinitis and asthma. Atopic Dermatitis is characterized by chronic, relapsing skin inflammation, a disturbance of epidermal-barrier function that culminates in dry skin, and IgE-mediated sensitization to food and environmental allergens. Immunologically, AD is characterized by excessive T-cell activation. T helper type 2 (Th2) cells produce interleukin (IL)-4, IL-5 and IL-13; and activate eosinophils, basophils and mast cells, as well as immunoglobulin E (IgE)-producing B cells, which are involved in allergic reactions.

### **3.2 Rationale for Treating Atopic Dermatitis with Tralokinumab**

Tralokinumab, a fully human monoclonal antibody, specifically neutralizes interleukin-13, a key cytokine driving peripheral inflammation in atopic dermatitis (AD). In phase II studies, tralokinumab combined with topical corticosteroids provided early and sustained improvements in AD signs and symptoms. In two 52-week, randomized, double-blind, placebo-controlled, phase III trials, ECZTRA 1 and ECZTRA 2, adults with moderate-to-severe AD were randomized (3 : 1) to subcutaneous tralokinumab 300 mg every 2 weeks (Q2W) or placebo. Tralokinumab monotherapy was superior to placebo at 16 weeks of treatment and was well tolerated up to 52 weeks of treatment. Dupilumab, a parenterally administered inhibitor of IL-4 and IL-13, is the first biologic drug approved for use in adults with moderate-to-severe atopic dermatitis. While Phase III trials showed improvement in AD symptoms and itch for patients with atopic dermatitis, many patients fail to achieve and/or maintain satisfactory efficacy, have an intolerance to dupilumab treatment or are unable to continue treatment related to insurance coverage. This study aims to explore the effectiveness and safety of tralokinumab (ADBRY) in patients previously exposed to dupilumab for atopic dermatitis.

## **4. STUDY OBJECTIVE**

To explore the effectiveness and safety of tralokinumab in subjects who have previously used dupilumab for the treatment of moderate-to-severe atopic dermatitis

## **5. INVESTIGATIONAL PLAN**

### **5.1 Overall Study Design and Plan**

20 adult subjects with moderate-to-severe atopic with previous exposure to dupilumab will receive tralokinumab loading dose of 600mg (4 150mg syringes) at week 0 followed by tralokinumab 300mg (2 150mg syringes) Q2W for 24 weeks.

### **5.2 Study Population Criteria**

Males and females  $\geq$  18 years of age with moderate-to-severe atopic dermatitis.

#### **5.2.1 Inclusion Criteria**

Patients who meet all of the following criteria will be enrolled in the study:

1. Male or female adults  $\geq$  18 years of age.
2. All participants must have prior treatment with dupilumab for atopic dermatitis meeting one of the following conditions:

- Participants who stopped dupilumab treatment due to non-response, partial response, loss of efficacy must have been previously treated with dupilumab for at least 12 weeks.
  - Participants who stopped dupilumab treatment due to intolerance or AEs to the drug may enter the study with no required prior length of dupilumab treatment. AE's must be resolved prior to 1st tralokinumab dose.
3. Females of childbearing potential (FCBP) must have a negative urine pregnancy test at Baseline. FCBP who engage in activity in which conception is possible must use one of the approved contraceptive options: hormonal contraception; intrauterine device (IUD); tubal ligation; or partner's vasectomy; Male or female condom diaphragm with spermicide, cervical cap with spermicide, or contraceptive sponge with spermicide.
  4. Subject is a candidate for systemic therapy.
  5. Subject must be in general good health as judged by the Investigator, based on medical history, physical examination.
  6. Able and willing to give written informed consent prior to performance of any study-related procedures.

### **5.2.2 Exclusion Criteria**

Patients will NOT be enrolled in this study if they meet any of the following criteria:

1. Subjects with previous exposure to tralokinumab
2. Subjects with known or suspected hypersensitivity to tralokinumab or any of its excipients.
3. Women of childbearing potential who are pregnant, intend to become pregnant, or are lactating.
4. Use of tanning beds or phototherapy within 4 weeks of baseline
5. Use of systemic therapies (systemic steroids, cyclosporine, oral JAK inhibitors etc.) for atopic dermatitis within 4 weeks
6. Patient non-compliant with Dupixent dosing based on investigator discretion.
7. Subjects who have received live vaccine within 4-weeks prior to Baseline or who intend to receive live vaccine during the study.
8. Active or acute infection requiring systemic antibiotics within 2 weeks of baseline visit.

9. Use of any investigational drug within 8 weeks prior to Baseline or within 5 pharmacokinetic/pharmacodynamic half-lives, if known (whichever is longer).
10. Any clinically significant (as determined by the investigator) cardiac, endocrinologic, pulmonary, neurologic, psychiatric, hepatic, renal, hematologic, immunologic disease, or other major disease that is uncontrolled.

### **5.3 Source of Subjects and Recruitment Methods**

The Investigator will manage the recruitment of subjects upon approval of the study by the Institutional Review Board. Subjects may be recruited from internal patient lists and outside IRB approved advertisements.

### **5.4 Subject Enrollment and Treatment Assignment**

20 subjects of either gender with moderate-to severe atopic dermatitis will be enrolled to receive open-label tralokinumab

## **5.5 STUDY TREATMENT**

### **5.5.1 Tralokinumb (ADBRY)**

#### **5.5.1.1 Tralokinumab Description**

Tralokinumab ADBRY is an interleukin-13 antagonist indicated for the treatment of moderate-to-severe atopic dermatitis in adult patients whose disease is not adequate controlled with topical prescription therapies or when those therapies are not advisable. ADBRY can be used with or without topical corticosteroids.

#### **5.5.1.2 Tralokinumab Dosing Schedule**

For the initial 600 mg dose, administer each of the four ADBRY 150 mg injections at different injection sites within the same body area. For the subsequent 300 mg doses, administer the two ADBRY 150 mg injections at different injection sites within the same body area.. Acceptable injection sites are thighs, abdomen >2 inches from the naval, or the upper arm (administered by medical staff or a caregiver). Subjects may come to the site for site staff to administer IP if they choose not to self-inject.

#### **5.5.1.3 Tralokinumab Dosage Adjustments**

If an adverse event that is thought to be related to tralokinumab and is not alleviated by symptomatic intervention, tralokinumab may be temporarily or permanently discontinued. If an adverse event causes the delay of administering tralokinumab, the dose may be

administered once the event has resolved or is stable in the opinion of the investigator. If an Q2W week dose is missed, the patient should administer the injection within 7 days from the missed dose and then resume the patient's original schedule. If the missed dose is not administered within 7 days, instruct the patient to wait until the next dose on the original schedule. Subjects who permanently discontinue tralokinumab under this protocol should receive standard care of atopic dermatitis treatment as prescribed by their physician.

